**Document History – Changes compared to previous final version of SAP**

Date	Time point	Reason for update	Outcome for update	Section and title impacted (Current)
03-Nov-2017	final in CREDI	N/A	N/A - First version	N/A
21-Jan-2020	Updates prior to DBL	Amendment 1	
Corrected definition of fever temperature for other routes from 38.3 to 38.0
 
Added note for tail of KM plots
 
Added that treatment failure definitions are based on P. falciparum asexual counts
 
Extended definition of LCF and LPF with respect to fever definition for other routes
 
Adapted condition of parasite clearance by Day 7 from definition of cures at Day 15/29 and from definition of event date for KM
 
Adapted definition of Analysis Sets to be consistent with Table 5-9
 
Added non-PD criterion to definition of PK analysis set
 
Removed category 'Mixed-infection' from demographic variable P. falciparum species, as mixed infections are not allowed
 
Removed shift tables
 
Adding note for handling Lab values beyond detection limit
 
Added 'New' to ECG criteria based on absolute values only
 
Harmonized definition of subjects excluded from FCT with respect to tables/figures
	
Section 2.3.2 and 2.8.3.2
 
Section 2.1.1
 
Section 2.1.1.1
 
Section 2.1.1.1 + Section 2.7.2.1
 
Section 2.2
 
Section 5.6, Table 5-9
 
Section 2.3.2
 
Section 2.8.2
 
Section 2.8.3.1
 
Section 2.7.2.3

Date	Time point	Reason for update	Outcome for update	Section and title impacted (Current)
			Adapted visit window for analysis timepoint for 4 hrs due to gap	Section 5.1.4 (Table 5-6)
			Clarified baseline derivation as assessments at treatment start datetime should be included	Section 2.1.1 & Section 5.1.4 (Table 5-7)
			Changed condition of clearance of initial infection for recrudescence/reinfection	Section 2.7.2.4/2.7.2.5
			Removed QTcB	Section 2.8.1.1/2.8.3.1
			Added derivation of study day for subjects that are randomized but not treated	Section 2.1.1
			Added HR to in-text table	Section 2.8.1.1
			Removed table for MH contributing to liver dysfunction	Section 2.3.1
			Changed threshold in step 2 (ii) to 500 such that algorithm fits to inclusion criterion 3	Section 2.13
			Added Lumefantrine	Section 2.9
			Added T1/2 to list of PK parameters	Section 2.9
			Removed visit window for time point 36 hrs for PK and adapted preceding and subsequent visit windows	Section 5.1.4, Table
		Protocol amendment	Adapted section according to protocol amendment; added new figure 1-1	Section 1.1
			Added two new treatment groups to list	Section 2.1.1
			Adapted sections according to protocol amendment	Section 2.15/3.2
			Added link to final list of prohibited medications	Section 5.2
07-Apr-	Updates	Addendu	Added subgroup of high baseline	Section 2.2.1

---

Date	Time point	Reason for update	Outcome for update	Section and title impacted (Current)
2020	after DBL	m 1	parasitaemia	
				
			Removed analysis on PPS	Section 2.3.2
				

---

## List of abbreviations

AE	Adverse event
ATC	Anatomical Therapeutic Classification
AUC	Area Under the Curve
bid	bis in diem/twice a day
CSR	Clinical Study report
CTC	Common Toxicity Criteria
CTCAE	Common Terminology Criteria for Adverse Events
DMC	Data Monitoring Committee
FAS	Full Analysis Set
eCRF	Electronic Case Report Form
IVR	Interactive Voice Response
IWR	Interactive Web Response
MedDRA	Medical Dictionary for Drug Regulatory Affairs
NCI	National Cancer Institute
o.d.	Once Daily
OS	Overall Survival
PFS	Progression-Free Survival
PK	Pharmacokinetics
PPS	Per-Protocol Set
PRO	Patient-reported Outcomes
qd	Qua'que di'e / once a day
QoL	Quality of Life
RAP	Report and Analysis Process
RECIST	Response Evaluation Criteria in Solid Tumors
SAP	Statistical Analysis Plan
SOC	System Organ Class
TFLs	Tables, Figures, Listings
WHO	World Health Organization
ETF	Early treatment failure
LPF	Late parasitological failure
LCF	Late clinical failure
SRC	Safety Review Committee
FCT	Fever clearance time
PCT	Parasite clearance time

## 1 Introduction

The purpose of the Statistical Analysis Plan (SAP) is to describe the implementation of the statistical analysis which is planned in the protocol. The study has 6 cohorts: Cohort 1, 5, 6 with 2 arms and Cohort 2, 3, 4 with 3 arms each. Proceeding to next cohort depends on the interim safety review outcome done by the safety review committee (SRC) which will happen at predefined time points and is outlined in section 2.15 below. A single database will suffice for all the cohorts. The clinical study report will be prepared after the final database lock (DBL) at the end of all cohorts on the basis of this SAP. This single SAP will be used for the analysis of data collected for each cohort and the pooled analysis of all the cohorts together. The statistical method in this SAP will be used to execute a separated SRC TFL shells by [REDACTED] for Interim Safety review if required.

### 1.1 Study design

This will be a multicenter, open label, randomized, dose escalation study to evaluate the hepatic safety and tolerability of KAE609 in adult patients ( $\geq 18$  years and  $\geq 45$  kg bodyweight) with uncomplicated malaria caused by *P. falciparum*.

Starting dose of KAE609 will be a single dose of 10 mg and following acceptable safety results in the 10 mg treatment arm, the dose of KAE609 will be increased stepwise up to a single dose of 225 mg and multiple doses of 50 mg (QD x 3 days) according to schedule below ([Figure 1-1](#)).

Based on the safety pattern observed in previous studies with KAE609, liver function test (LFT) parameters, if they rise, are expected to peak within 14 days of treatment. Hence, the decision to escalate to next cohort with higher doses will be based on the criteria as specified in the table below ([Table 1-1](#)):

[figure not shown]
**Table 1-1 Decision criteria for dose escalation based on LFT results with KAE 609**

LFT parameter	Baseline	Maximum post baseline value	Decision to escalate to next cohort
ALT/AST	Within ULN	< 2 times ULN (from Day 1 to Day 15 )	Escalate to next cohort after notification to safety review committee, after all the patients in the cohort have been followed for at least 14 days post treatment (study Day 15).
	> 1 to $\leq 1.5$ ULN	< 2 times baseline (from Day 1 to Day 15 )	
ALT/AST	Within ULN	$\geq 2$ to < 3 times ULN (from Day 1 to Day 15 )	Escalate to next cohort based on review of liver safety (and any other relevant data) by safety review committee, after all the patients in the
	> 1 to $\leq 1.5$ ULN	$\geq 2$ to < 3 times baseline (from Day 1 to Day 15 )	

			cohort have been followed for at least 28 days post treatment ( Study Day 29 )
ALT/AST	Any baseline value	
≥ 2 Grade (CTCAE grades) increase from baseline (at any time point during the study) in:
 
 
- 2 patients in a 10 patient cohort (Cohorts 1 and 2)
 
or
 
- 3 patients in a 20 patient cohort (Cohorts 3 and 4, 5 and 6)
 
	
Suspend recruitment and initiate review of liver safety (and any other relevant data) by safety review committee.
 
Any further progression of the study is based on the decision by the safety review committee

In consultation with the safety review committee, Novartis can suspend recruitment and trigger safety review any time based on safety signals including any potential Hy’s law case. Based on the pre-specified criteria (Table 3-1) and the review of the liver safety data by a safety review committee, the recruitment in Cohort 5 may be stopped and a lower dose of KAE609 i.e. 110 mg may be selected for Cohort 6. The study could be stopped after Cohort 5 if there is no added advantage for dosing the patients with 225 mg single dose from the perspective of future clinical development of KAE609 and its subsequent use in clinical practice.

**Figure 1-1 Study KAE609A2202 diagram**

Given the expected sub-therapeutic efficacy of the doses of KAE609 in the first 2 cohorts, a smaller number (N=10) of patients will be included (10 mg Single Dose (SD), 25 mg SD and 10 mg 3 Days) to detect potential LFT increases. In the subsequent cohorts a higher number (N=20) of patients will be included. All patients will be followed up for 4 weeks with close monitoring in an inpatient setting for at least the first 3 days (Study Day 4) for efficacy and safety followed by outpatient monitoring up to Study Day 29.

Patients will be randomized to KAE609 vs Coartem in a ratio of 1:1 in cohort 1. In cohort 2, SD KAE vs QD KAE609 vs Coartem will be randomized in the ratio of 1:1:1. In Cohorts 3

and 4 the SD KAE609 vs QD KAE609 vs Coartem will be randomized in the ratio of 2:2:1. In Cohorts 5 and 6 the SD KAE609 vs Coartem will be randomized in the ratio 2:1. There are no stratification factors in this study.

Visits to assess safety and efficacy will be scheduled during the follow-up period as described in the assessment schedule table in protocol.

The safety of entire study will be monitored by the Safety Review Committee.

## 1.2 Study objectives and endpoints

**Table 1-2 Objectives and related endpoints**

Objective(s)	Endpoint(s)

Primary Objective(s)
 
 
To characterize hepatic safety aspects of single- and multiple ascending doses of KAE609 in adult malaria patients
 
	
Endpoint(s) for primary objective(s)
 
 
At least 2 CTCAE grades increase from baseline in ALT or AST during the 4 week study period
 

Secondary Objective(s)
 
 
To evaluate overall safety and tolerability of KAE609.
 
To assess key PK parameters following treatment with KAE609.
 
To assess the efficacy of KAE609 in patients with uncomplicated falciparum malaria.
 
To assess recrudescence after single and multiple doses of KAE609
 
	
Endpoint(s) for secondary objective(s)
 
 
Standard safety/tolerability assessments (AE incidence and severity, vital signs, ECG, laboratory abnormalities)
 
PK parameters such as AUC, Cmax, Tmax, T1/2 etc.
 
PCR-Uncorrected adequate clinical and parasitological response (ACPR) and PCR-Corrected ACPR at Days 15 and 29 (i.e., 14 and 28 days post-dose)
 
Parasite and Fever Clearance Times (PCT and FCT) before rescue medication is given
 
Incidence rate of recrudescence at Day 29
 

## 2 Statistical methods

### 2.1 Data analysis general information

Data will be analyzed by [REDACTED] on behalf of Novartis for the interim safety assessment and after final DBL using SAS version 9.4 according to the data analysis presented in section 9 of the study protocol which will also be available in [Appendix 16.1.1 of the CSR](#). Important information is given in the following sections and details will be provided, as applicable, in [Appendix 16.1.9 of the CSR](#).

At the end of trial, full statistical analyses will be performed by cohort and treatment group. Coartem data from all cohorts will also be pooled.

Any data analysis carried out independently by the investigator should be submitted to Novartis before publication or presentation.

Data analyses required for the study SRC meeting will be analyzed by the third party vendor ([REDACTED]). The outline of the SRC Review analysis plan is presented in the SRC charter and will be detailed in the SRC TFL shells. A separate SAP for SRC is not needed since the statistical methods for SRC are same as those in this SAP.

Information on visit windows, imputation rules and the methods of efficacy and safety analyses is given in the sections to follow and details will be provided, as applicable, in [Appendix 16.1.9 of the CSR](#). This SAP covers the methods for both planned interim safety review and the final analysis.

Unless otherwise stated, summary tables/figures/listings will be on all patients included in the population under consideration.

Categorical data will be presented as frequencies and percentages. For continuous data, n, mean, standard deviation, median, 25th and 75th percentiles, minimum, and maximum will be presented. Additionally, geometric mean will be presented for PK parameters which may be better described using the lognormal distribution.

Unless otherwise stated, p-values will be provided for two-sided alternative hypotheses and presented with up to 4 significant digits after decimal place; confidence intervals will be presented with up to 2 significant digits after decimal place.

Since the randomization is not stratified, statistical analysis will not be stratified. For pooled analyses, coartem patients will be pooled from all the cohorts and compared with patients from different KAE doses.

#### 2.1.1 General definitions

**Study treatment:** KAE609 is the investigation treatment whereas Coartem® will serve as control. They are referred to as study treatments in the document.

Summary results will be presented by cohort and treatment group. Besides, a pooled Coartem group from all cohorts will be presented from all tables as applicable. The following abbreviated treatment group labels will be used as the column headers in the CSR outputs:

- KAE609 10 mg SD

- KAE609 10 mg QD 3 days
- KAE609 25 mg SD
- KAE609 25 mg QD 3 days
- KAE609 50 mg SD
- KAE609 50 mg QD 3 days
- KAE609 75 mg SD
- KAE609 150 mg SD
- KAE609 225 mg SD or KAE609 110 mg SD
- Coartem
- Pooled Coartem

**Baseline:** The last measurement made prior to and including administration of the first dose of study treatment. Note this may include measurements taken on the day of randomization (e.g. lab, ECG, vital signs). If a patient did not receive any dose of study treatment then the randomization date will be used as the date of first dose of study treatment.

**Study day:** Study day will be calculated with respect to the first dose of study treatment. The first day of administration of study treatment (first dose) is defined as Day 1. Day -1 will be the day before Day 1. Day 0 does not exist. If a patient did not receive any dose of study treatment then the randomization date will be used as the date of first dose of study treatment.

For assessments collected on or after Day 1, study day = date of assessment – date of first dose of study treatment + 1.

For assessments collected prior to Day 1, study day = date of assessment - date of first dose of study treatment.

At the end of trial, full statistical analyses will be performed by cohort and treatment group. Coartem data from all cohorts will also be pooled.

Tail of KM plots: Since the tail of KM plots after the day of last planned assessment is not reliable due to small numbers of patients at risk, the time to event will be truncated to the planned last day (Day 29) regardless of censoring.

#### 2.1.1.1 Definition for treatment failures

All definitions of treatment failures are based on *P. falciparum* asexual counts.

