9.5.1.1 PCR-corrected ACPR and uncorrected ACPR

At each visit, the ACPR rate with 95% confidence intervals will be provided using the Pearson-Clopper method for each treatment group by cohort.

Data will be handled as follows:

- Treatment failures after 7 days (i.e., Study Day 8) due to reinfection based on PCR genotyping are not considered as failure for PCR-corrected analyses.
- For parasitological uncorrected ACPR, patients will be treated as failure on and after the visit when a new infection (i.e., reinfection) with *P. falciparum* or other species is detected.
- Patients who received rescue medication for the treatment of *P. falciparum* malaria (except for the treatment of a new infection) will be considered treatment failures. Patients who received other concomitant medication having an effect on malaria for reasons other than rescue therapy e.g., for the treatment of *P. vivax* (e.g., primaquine, certain antibiotics (sulfonamides, tetracycline, etc.)) will be considered in the analysis as if they had not taken the drug.
- Patients will be counted as failure at a visit (e.g., Study Day 15, etc.) if (a) they did not have a parasite count i.e., missing parasite count at that visit unless these patients could be classified as cured based on absence of parasitaemia (parasite count = 0) at a later time (e.g., Study Day 29), or (b) they did not have valid PCR evaluations at baseline and the visit if parasitaemia was present at that time (e.g., Study Day 15).

In addition, PCR-corrected ACPR rate will be calculated and plotted using the Kaplan-Meier method ([Stepniewska and White 2006](#); [WHO 2016](#)) for each treatment group by cohort in the FAS. Treatment failure is the event for analysis and patients without Study Day 29 data and treatment failure is considered as censored instead of treatment failure. The PCR-corrected ACPR rate at Study Day 29 is estimated by the survival function at Study Day 29. Patients who had a new infection (i.e., reinfection) with *P. falciparum* or other species without *P. falciparum* recrudescence on or after Study Day 8 will be censored at the time of the first PCR that indicate the infection; patients who took antimalarial medications for reinfection or reasons other than

rescue medication given for *P. falciparum* related treatment failure will be censored at the first time of such antimalarial medications; other patients without treatment failure will be censored at the time of last parasitaemia assessment.

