### **Uncorrected ACPR at Day X where X=15 and 29**

- A patient is considered as non-responder at Day X if the patient experiences an ETF, LCF or LPF from Day 5 to Day X.
- A patient is also considered as non-responder if the parasitaemia is not cleared by Day X unless the patient discontinues the study prior to Day X without ETF, LCF, or LPF in which case the response is considered as missing.

- A patient is considered as responder (Uncorrected ACPR) at Day X if the patient is not classified as a non-responder at Day X and the patient has a malaria blood film showing absence of parasitaemia at Day X or later if Day X is missing.
- The response for a patient is considered as missing/undertermined if the patient is not classified as a non-responder and the malaria blood film result at Day X is missing and not followed by a subsequent negative result.

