### **Handling of missing values/censoring/discontinuations**

Data will be handled as follows:

- Patients with presence of parasitaemia which was determined to be reinfection on Day 8 or later will be counted as responders for PCR corrected ACPR and as non-responder for PCR uncorrected ACPR from the day of test
- Patients with presence of parasitaemia which cannot be determined to be recrudescence or reinfection due to missing PCR corrected/uncorrected data will be counted as non-responders from the day of test
- Patients with missing/undetermined responses at a visit due to missing blood smear data at the visit will be counted as non-responders (PCR corrected or uncorrected) unless there is a later blood smear test indicating no parasitemia
- Patients who received non rescue anti-malarial medication will be considered in the analysis as if they had not taken the anti-malarial drug.

In addition, PCR-corrected and uncorrected ACPR rate will be calculated and plotted using the Kaplan-Meier method for each treatment group by cohort in the FAS.

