##### **Rule for censoring:**

The following censoring rules will be applied to the patients who were not non-responders

- Patients who received non-rescue anti-malaria medication will be censored at the first time of anti-malaria medication;
- other patients will be censored at the time of last parasitemia assessment.

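### SAP 2.1.1.1 rests uncorrected-ACPR non-response on *P. falciparum* counts, in conflict with protocol 9.5.1.1 and with the SAP's own species-neutral rules for new infections

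*SAP*

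**What the plan says.** **Protocol 9.5.1.1** sets this rule for the uncorrected endpoint: "patients will be treated as failure on and after the visit when a new infection (i.e., reinfection) with *P. falciparum* or other species is detected".

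**SAP, pointing to *P. falciparum* only**
- 2.1.1.1 opens with "All definitions of treatment failures are based on *P. falciparum* asexual counts". The document history lists this as an addition in the January 2020 update.
- 2.1.1.1, Uncorrected ACPR: "A patient is considered as non-responder at Day X if the patient experiences an ETF, LCF or LPF from Day 5 to Day X". Uncleared parasitaemia is the other route to non-response. A responder is a patient who is not a non-responder and for whom "the patient has a malaria blood film showing absence of parasitaemia at Day X or later if Day X is missing". There is no rule for other species.
- 2.7.2.1.2, the Kaplan-Meier analysis of uncorrected ACPR, takes its event from the Day 29 non-responder definition in Section 2.1. It has no rule for other species either.

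**SAP, naming no species or including others**
- The Note at the end of the ACPR definitions in 2.1.1.1 makes parasitaemia found later than seven days from first dosing a non-response for uncorrected ACPR. It names no species.
- 2.7.2.1, data handling, counts parasitaemia determined to be reinfection on Day 8 or later "as non-responder for PCR uncorrected ACPR from the day of test". It names no species.
- 2.7.2.1.1, the censoring rules for PCR-corrected ACPR, uses reinfection to cover *P. falciparum* and other species.

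SAP Section 4 reports no change to the protocol's analyses.

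**The concern.** Uncorrected ACPR at Days 15 and 29 is a listed secondary endpoint, and under the protocol a recurrence of any species counts against it. The SAP dropped the protocol's reference to other species from every rule it wrote for uncorrected ACPR, and then added a sentence limiting failure to *P. falciparum* counts. A programmer who follows that sentence and the bullets below it can reach the opposite classification from the protocol. One who follows the Note or the data-handling rule reaches the protocol's answer. The reported rate would then depend on which part of the SAP was coded. The proportion and the Kaplan-Meier estimate could even classify the same patient differently, and Section 4 would not tell the reader that anything had changed.

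**Working it through.** The plan states no figure that depends on this rule, so there is none to reproduce. The check is to trace one patient through each rule and then size the effect.

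**Can the case arise?** Yes. Protocol 6.4.1 has the microscopist note any other species found on follow-up films.

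**Trace.** *P. falciparum* clears early, the Day 22 film shows another species, and the Day 29 film is negative.

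| Rule followed | Day 29 proportion | Kaplan-Meier |
|---|---|---|
| Protocol 9.5.1.1 | Failure from Day 22 | Protocol describes this only for PCR-corrected ACPR |
| SAP 2.1.1.1 opening sentence with the Uncorrected ACPR bullets | No LCF or LPF, film negative: responder | Not an event; censored |
| SAP 2.1.1.1 Note | Non-responder | Event |
| SAP 2.7.2.1 reinfection rule, with the word used as in 2.7.2.1.1 | Non-responder from Day 22 | Depends on whether the event definition takes in this rule |

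On the second row, the censoring date comes from 2.7.2.1.2. If another antimalarial was given, "Patients who received non-rescue anti-malaria medication will be censored at the first time of anti-malaria medication". Otherwise it is the last parasite assessment.

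The last row is open on two counts. SAP 2.7.2.5 requires PCR confirmation of reinfection, and the Note leaves the split between recrudescence and new infection to the central laboratory, so a finding on the film alone may not reach the rule. Also, the Kaplan-Meier event definition refers back to Section 2.1, which contains the Note but not the 2.7.2.1 handling rule.

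If the other species is still on the Day 29 film, the bullets give responder only if absence of parasitaemia is also read as *P. falciparum* only. That bullet does not say so.

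**Size.** Inputs: planned KAE609 arms of 10 (Cohorts 1 and 2) and 20 (later cohorts), from SAP 1.1; exact Clopper-Pearson 95% intervals, from SAP 2.7.2.1. Assumption: k = 0, 1 or 2 such patients in an arm, everyone else a responder.

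- Shift per patient = 1/n: 1/20 = 5 points, 1/10 = 10 points.
- Interval for x of n: lower limit = 2.5% quantile of Beta(x, n − x + 1); upper limit = 97.5% quantile of Beta(x + 1, n − x), set to 1 when x = n.

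| n | k | Falciparum-only reading | Protocol rule |
|---|---|---|---|
| 20 | 0 | 100% (83.2–100) | 100% (83.2–100) |
| 20 | 1 | 100% (83.2–100) | 95% (75.1–99.9) |
| 20 | 2 | 100% (83.2–100) | 90% (68.3–98.8) |
| 10 | 1 | 100% (69.2–100) | 90% (55.5–99.7) |
| 10 | 2 | 100% (69.2–100) | 80% (44.4–97.5) |

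Kaplan-Meier at Day 29, n = 20, k = 1: with the patient censored there are no events, so the estimate is 100%. With an event on Day 22 and all 20 still at risk, it is 1 − 1/20 = 95%.

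**The case against.** The strongest reply is that the SAP already makes these patients non-responders. The Note in 2.1.1.1 says so without naming a species. The 2.7.2.1 reinfection rule says so too once reinfection is given the meaning it has in 2.7.2.1.1. The Note also separates responder and non-responder from the failure categories, so the *P. falciparum* sentence may govern only ETF, LCF and LPF. Moreover, SAP 2.1 commits the analysis to Section 9 of the protocol, and the *P. falciparum* sentence is disclosed in the document history.

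Much of this stands. A reader might infer that the SAP turns every non-falciparum recurrence into a response. The documents do not support that: they leave the classification unsettled, and they contain no program that would show how it was coded.

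The reply does not remove the conflict. The uncorrected non-responder bullet is written in terms of ETF, LCF and LPF, so it inherits the species limit. The wording that includes other species belongs to censoring for the PCR-corrected analysis, and the matching list for the uncorrected analysis omits it. A general pledge to follow the protocol does not tell a programmer which of two SAP rules to apply.

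A reader might also see a SAP departure in "Patients who received non rescue anti-malarial medication will be considered in the analysis as if they had not taken the anti-malarial drug". It is not one: protocol 9.5.1.1 likewise disregards drugs with antimalarial effect taken for reasons other than rescue, and gives treatment of *P. vivax* as an example.

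Finally, the event may be rare: mixed infections are excluded at entry and follow-up is four weeks. That bears on the size of the effect, not on whether the rule is clear.

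**Conclusion.** The concern holds as a conflict of definitions. The *P. falciparum*-only sentence in SAP 2.1.1.1, carried into the uncorrected ACPR bullets, contradicts protocol 9.5.1.1 and does not fit the SAP's own Note and reinfection rule. A patient with a new non-falciparum infection on Day 8 or later and a negative Day 29 film can be classed either way, and can be either censored or an event in the uncorrected Kaplan-Meier analysis.

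The size is 5 or 10 points per patient, by arm size. The number of such patients is unknown from the documents; 0 to 2 per arm is only an illustration, and at zero nothing changes. The endpoint is secondary and descriptive, with no planned comparison against Coartem. The primary hepatic endpoint and the power table do not depend on it. It should be corrected, but it does not threaten the study's main conclusion.

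**What to change.** In SAP 2.1.1.1 (Uncorrected ACPR), 2.7.2.1 (data handling) and 2.7.2.1.2 (event and censoring rules), state that new asexual parasitaemia of any *Plasmodium* species on or after Day 8 is non-response for uncorrected ACPR, with the first positive film as the event date. Keep *P. falciparum* counts for ETF, LCF, LPF and PCR-corrected ACPR, and say that the opening sentence of 2.1.1.1 is limited to those. The Day 8 start follows the SAP's reinfection rule; the protocol sentence sets no starting day, so the sponsor should confirm it.

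If the *P. falciparum*-only rule is what the sponsor intends for uncorrected ACPR, keep it, bring the Note and 2.7.2.1 into line, and list the departure from protocol 9.5.1.1 in SAP Section 4.

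The cost is a few sentences and one derivation, since species is already noted on the films. The uncorrected rate becomes slightly less favourable if any such case occurs.
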